13.1.6 Vaccinations during MTX therapy

Live vaccines, such as the vaccine for yellow fever, are contra-indicated in people taking oral MTX. There is no contra-indication to receiving mRNA vaccines, including currently available vaccinations against SARS-CoV-2.

Current national guidance in regard to vaccinations during MTX therapy must be followed. At the time of preparation of this protocol (October 2022), the British Society for Rheumatology states on its website: “In response to the [VROOM study \(44\)](#), adult rheumatology participants, who are stable on methotrexate, may consider stopping methotrexate after booster vaccination for COVID-19 for 2 weeks (skipping 2 doses of methotrexate). There is no need to stop prior to vaccination. There is a small risk of flare. This has been shown to improve vaccine response to COVID-19.” (45)

13.1.7 Use of Proton-Pump Inhibitors during MTX therapy

Proton pump inhibitors may be prescribed alongside low-dose MTX if clinically indicated.

13.1.8 Use of other Experimental Drugs during MTX therapy

Use of any other experimental drug during MTX therapy is not permitted.

13.1.9 Methotrexate Dosing and Frequency

For the treatment of rheumatic conditions oral MTX must be prescribed **weekly** (low-dose). Daily MTX administration would be classed as high-dose and carries a high risk of toxicity

The STERLING trial specifies a Starting Dose, Target Dose and Minimal Dose for MTX. Due to inter-individual variation in oral MTX bioavailability and toxicity, dose titration is used to achieve a maximum tolerated dose of MTX for each participant, which will be between 7.5mg weekly and 25mg weekly.

The participant's GP should be informed in writing of all dose escalations, reductions and other modifications and should be requested to update this dose information on the participant's healthcare record.

The Starting Dose, Target Dose and Minimal Dose are specified in Table 1.

In the following discussions, "frailty" is not specifically defined and will be assessed at the physician's discretion on clinical grounds, taking into account all relevant circumstances. For example, some participants with multiple long-term conditions sufficient to cause significant limitations of daily activities or frequent falls might be deemed as clinically frail.

Methotrexate Dosing:	Dose, reason
Starting Dose	15mg weekly for most participants 10mg weekly in frailty (physician's discretion) or renal disease i.e. stage 3 chronic kidney disease defined as eGFR <60mg/ml (value provided by local laboratory)
Target Dose (if tolerated)	25mg weekly is the maximum permitted Recommend 15mg weekly for participants with renal disease i.e. stage 3 chronic kidney disease defined as eGFR <60mg/ml (value provided by local laboratory)
Minimal Dose	7.5mg weekly If this is not tolerated, stop MTX and folic acid, consider starting LEF
Maximum Tolerated Dose	Established for each individual by dose titration; must not exceed 25mg weekly.

Table 1.

13.1.10 Methotrexate Starting Dose

The Starting Dose of MTX will generally be 15mg weekly. This may be reduced to 10mg weekly at the physician's discretion for individuals with relevant co-morbidities e.g. frailty or significant renal disease i.e. stage 3 chronic kidney disease defined as eGFR < 60mg/ml.

Participants may wish to delay their first MTX dose for up to two weeks after the baseline visit.

Participants will remain on the Starting Dose until at least the week 4 follow-up telephone consultation with the site team.

13.1.11 Methotrexate Target Dose

The earliest timepoint for potential dose escalation will be following the week 4 telephone assessment, but may occur following any of the telephone assessments up to the week 26 clinical assessment.

Dose escalation should only be performed once the latest DMARD monitoring blood tests (see section 13.1.2) have been checked to assess for any biochemical/haematological abnormalities (see section 13.4.1) and where the participant is not experiencing other intolerable toxicities e.g. nausea.

If DMARD monitoring is satisfactory (see section 13.4.1), participants should be advised to increase their MTX dose in line with their Target Dose. The Target Dose is 25mg weekly for most participants, but prescribers should consider reducing the Target Dose to 20mg weekly for participants with renal dysfunction or frailty.

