7.5.2 Potential for drug interactions

The PI will be responsible for prescribing DMARD. At the time the DMARD is initiated, the PI will check for relevant interactions of the DMARD with any concomitant medications. They will also communicate any starting or stopping of DMARD with the participants GP in a timely fashion.

DMARD should normally be paused (temporarily stopped) during a course of antibiotics that might be prescribed for intercurrent infection. For mild, uncomplicated infections in the community that have resolved by the end of

the course of antibiotics, and where broad-spectrum antibiotics have not been used, DMARD can generally be restarted after the antibiotics have finished. However, if there is any doubt, the participant and/or GP may contact the site for advice on when to restart the DMARD after completion of the course of antibiotics, depending on the infection type or severity, or if there are any other queries in relation to intercurrent infection.

MTX may accumulate in renal impairment. If acute deterioration in renal function occurs in a participant being prescribed MTX during the study, and the participant is in the community, GPs are asked via the trial specific GP letter to notify the site of this so that the MTX can be stopped, paused or dose-reduced by the site as necessary. If the participant is admitted to hospital then the admitting team will be at liberty to manage MTX dosing as clinically indicated in consultation with the rheumatology team.

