4. A medical condition other than PMR that has required >2 courses of systemic glucocorticoid treatment lasting 5 days or more, or any course lasting 30 days or more, during the year prior to randomization.
5. Giant cell arteritis (previous or current) in the opinion of the local investigator.
6. Rheumatoid arthritis, psoriatic arthritis or spondyloarthritis (previous or current) in the opinion of the local investigator
7. At the baseline visit active infection of sufficient severity to be a contra-indication to commencing methotrexate, in the opinion of the local investigator.
8. Participant taking concurrent trimethoprim-sulfamethoxazole at the time of the baseline assessments
9. Active gastric ulcer at the baseline visit in the opinion of the local investigator
10. Known prior history of a significant immunodeficiency syndrome, defined as an immunodeficiency severe enough to cause recurrent infections of frequency or severity that in the opinion of the investigator would preclude DMARD treatment
11. Known prior history of hereditary galactose intolerance, hereditary total lactase deficiency or hereditary disorder of glucose-galactose malabsorption
12. Current treatment with folate antagonists including trimethoprim-sulfamethoxazole
13. Other medical condition that in the opinion of the local investigator is severe enough to seriously compromise evaluation of the primary or key secondary endpoints
14. Treatment with any immunosuppressive therapy (conventional synthetic, targeted synthetic or biological DMARD) within 3 months prior to randomisation.
15. Treatment with any investigational drug in the last 4 months prior to the start of protocol treatment.
16. Unable to complete essential study procedures and communicate with study staff independently.
17. Participants must NOT fulfil any of the following within 6 weeks prior to baseline: Haemoglobin <10.0 g/dL; total white cell count <3.5 x10⁹/L; absolute neutrophil count <1.5 x10⁹/L; platelet count <100 x10⁹; ALT (alanine aminotransferase) or AST > 2 x upper limit of reference range for the laboratory conducting the test, eGFR (estimated glomerular filtration rate) <30ml/min

18. Evidence of respiratory disease on chest radiograph (performed during screening or within the 6 months prior to screening) of sufficient severity to be a contra-indication to commencing methotrexate, in the opinion of the local investigator.

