13.3.7 Leflunomide Starting Dose

The Starting Dose of LEF will generally be 10mg daily but may be reduced to 10mg alternate days for individuals with relevant co-morbidities, for example significant frailty, at the physician's discretion.

Participants will remain on this dose until at least the week 4 follow-up telephone consultation with the site team.

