13.3.8 Leflunomide Target Dose

The earliest timepoint for potential dose escalation will be following the week 4 telephone assessment but may occur following any of the telephone assessments up to the week 26 clinical assessment.

Dose escalation should only be performed once the latest DMARD monitoring blood tests and blood pressure (see section 13.3.4) have been checked to assess for any biochemical/haematological abnormalities and blood pressure has been taken to exclude hypertension (value should be below 140/90).

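### Section 13 advises two methotrexate targets (15mg and 20mg weekly) for participants with eGFR 30-59, and ties leflunomide titration to methotrexate's week 4 and week 26 limits

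*Protocol*

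**What the plan says.** **MTX target.** Section 13.1.9 points to Table 1 for the starting, target and minimal doses. Table 1 sets a ceiling of 25mg weekly and adds: "Recommend 15mg weekly for participants with renal disease", meaning stage 3 chronic kidney disease with eGFR below 60. Section 13.1.11 repeats 25mg as the usual target, then says "prescribers should consider reducing the Target Dose to 20mg weekly for participants with renal dysfunction or frailty". It gives no eGFR cut-off and does not refer to Table 1.

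**Who can enrol.** Exclusion 17 in section 8.2 removes "eGFR (estimated glomerular filtration rate) <30ml/min". The lower starting dose of 10mg weekly is available "for individuals with relevant co-morbidities e.g. frailty or significant renal disease i.e. stage 3 chronic kidney disease defined as eGFR < 60mg/ml". Section 7.5.2 warns that "MTX may accumulate in renal impairment".

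**LEF titration.** For MTX, 13.1.10 says "Participants will remain on the Starting Dose until at least the week 4 follow-up telephone consultation with the site team". For LEF, 13.3.7 says "Participants will remain on this dose until at least the week 4 follow-up telephone consultation with the site team", and 13.3.8 says escalation "may occur following any of the telephone assessments up to the week 26 clinical assessment", the same limit as 13.1.11 sets for MTX. LEF begins only once MTX has stopped (13.3.10), with a recommended wash-out of at least 2 weeks, extendable to 8 (13.3.1). A switch for inefficacy is allowed from 3 months at the maximum tolerated MTX dose (13.1.14). Section 7.3.2 provides for LEF to go up to 20mg daily in anyone who tolerates it.

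**The concern.** Two sites can each follow the protocol and take the same kind of participant, with eGFR 30-59, to different MTX targets. The drug is one that the protocol itself says can accumulate when renal function is poor. The telephone section (14.6), where escalation is discussed, sends staff to 13.1.11, which carries the 20mg advice, and not to Table 1, which carries 15mg.

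For LEF, a site cannot tell from 13.3.7 and 13.3.8 whether the weeks run from randomisation or from the first LEF dose. If they run from randomisation, the limits were written for a drug that starts at week 0 and have been applied to one that starts later. The hold may then protect nobody, and the chance to escalate may have gone before treatment begins.

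**Working it through.** **Renal target**

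Inputs: target 15mg (Table 1), target 20mg (13.1.11), maximum 25mg (Table 1), renal starting dose 10mg (Table 1 and 13.1.10), entry floor eGFR 30 (exclusion 17).

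- Group affected: eGFR below 60, less the excluded eGFR below 30, leaves 30-59. This is the only renal group that the dosing text defines.
- Ratio of targets: 20/15 = 1.33, so one third higher. Against the maximum: 15/25 = 60% and 20/25 = 80%.
- Planned increase from the 10mg start: 15 - 10 = 5mg under Table 1, 20 - 10 = 10mg under 13.1.11, twice as much.

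**Time origin for LEF**

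Section 7.4.1 times the in-person visits from randomisation. Visits are listed at weeks 12, 24, 36, 48 and 80 (14.2 and 14.7). None is at week 26, so the limit names a visit that does not exist, for MTX as well as LEF.

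**LEF hold, read in trial weeks**

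If MTX stops at week s and the wash-out lasts w weeks, the hold left when LEF starts is max(0, 4 - (s + w)).

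- w = 2: 2 weeks left if s = 0, 1 week if s = 1, none if s is 2 or more.
- w = 8: none for any s.
- w = 0 (the wash-out is recommended, not mandatory): none if s is 4 or more.

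**LEF escalation window, read in trial weeks**

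If the maximum tolerated MTX dose is reached at week m, and 3 months is taken as 13 weeks, the earliest LEF start after an inefficacy switch is m + 13 + w. I treat the window as open until week 26.

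| m | LEF start, w = 2 | LEF start, w = 8 | Window when LEF starts |
|---|---|---|---|
| 0 (starting dose is the maximum tolerated) | 15 | 21 | open |
| 4 | 19 | 25 | open |
| 8 | 23 | 29 | open, or closed with the long wash-out |
| 12 | 27 | 33 | closed |
| 24 | 39 | 45 | closed |

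The window is closed when m + 13 + w exceeds 26, that is when m exceeds 13 - w: after week 11 with a 2-week wash-out and after week 5 with an 8-week one. Taking 3 months as 12 weeks moves these points to weeks 12 and 6.

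A switch for intolerance after a single MTX dose at week 0 or week 2 gives LEF starts from 0 + 2 = 2 to 2 + 8 = 10, inside the window.

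**Related wording**

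- Section 7.3.2 names 10mg as the MTX dose below which to switch; 13.1.9 and 13.1.12 set the minimal dose at 7.5mg.
- Section 14.6 refers to section 13.2.8, which does not exist; LEF escalation is in 13.3.8.
- Table 1 and 13.1.10 print the eGFR threshold in mg/ml; exclusion 17 uses ml/min.
- Section 13.1.11 gives frailty a reduced target of 20mg; Table 1 gives it none.

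**The case against.** **On the renal target.** Table 1 is where the protocol says doses are specified, and its verb (recommend) is stronger than the one in 13.1.11 (consider). A careful prescriber might therefore settle on 15mg. Neither figure is mandated: each participant is titrated to a tolerated dose between 7.5 and 25mg weekly, escalation needs satisfactory blood tests and no intolerable toxicity, and dosing is reviewed in acute renal impairment. All of that stands and limits the risk. It does not remove the conflict. The limits in 13.4.1 cover liver enzymes and neutrophils but set no eGFR threshold, so the required checks do not decide between 15 and 20mg. One could reconcile the texts by taking renal dysfunction to mean something milder than stage 3 disease, but nothing in the protocol says so.

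**On LEF.** A sensible site may read week 4 as four weeks of LEF. The wording is permissive, and section 13.4 on withdrawal of treatment lets clinicians alter regimens at any time. Blood tests and blood pressure must be checked before any LEF escalation. On that reading little harm follows, but the site has to supply a time origin that the text does not give. The schedule's window of 2 weeks either side lets the week 24 visit fall as late as week 26, which may explain the number but does not create a week 26 assessment.

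**Stronger readings that the document does not support.**

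- A reader might infer that most inefficacy switchers would stay at the LEF starting dose. The protocol gives no distribution of time to maximum tolerated dose, so no proportion can be stated.
- A reader might add four weeks on LEF to the start dates above and conclude that escalation by week 26 is feasible only when the maximum tolerated dose is reached at week 4. That combines a hold counted from LEF start with a limit counted from randomisation, and it omits participants whose starting dose is already their maximum (LEF start at weeks 15-21).
- A reader might see a further conflict with 14.6, because calls at weeks 60 and 72 discuss escalation. Section 14.6 defers to the dosing sections and sets no window of its own.

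**Conclusion.** Both points hold, as internal inconsistencies in dosing text that should be fixed.

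The protocol advises 15mg and 20mg weekly for participants with eGFR 30-59, a difference of one third in target and a factor of two in the planned increase from a 10mg start. This rests on taking renal dysfunction in 13.1.11 to include stage 3 disease. That is an inference, but a reasonable one, since no other renal group is defined.

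LEF titration has no usable time origin. Read in trial weeks, the hold has usually expired before LEF starts. The escalation window has closed for inefficacy switchers who reach maximum tolerated MTX dose at about week 12 or later, which conflicts with 7.3.2. With an 8-week wash-out it closes for earlier cases too. These dates assume 3 months of about 13 weeks and the 2-8 week wash-out.

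The 10mg against 7.5mg difference is only a wording mismatch, because MTX may be stopped for toxicity at any time. Sample size, alpha and the intention-to-treat primary analysis are unaffected.

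**What to change.** - Make Table 1 the single source for MTX targets: 15mg weekly for eGFR below 60, confirmed by the clinical team, with the 20mg frailty target added. Have 13.1.11 refer to Table 1 and state no separate renal figure.
- Correct the eGFR unit to ml/min in Table 1 and 13.1.10.
- In 13.3.7 and 13.3.8, count from LEF start: at least 4 weeks at the starting dose, then escalation at any scheduled contact once the blood and blood pressure checks are done, with no week 26 limit.
- In 13.1.11, change week 26 to week 24.
- In 14.6, change the cross-reference from 13.2.8 to 13.3.8.
- In 7.3.2, use the 7.5mg minimal MTX dose.

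The cost is a text amendment and a site memo, with no added procedures. It should be coordinated with the UK protocol, because the data are pooled (24.2.1). The downside is that some participants with eGFR 30-59 who could have tolerated 20mg may receive less MTX, which is why the clinical team should confirm the 15mg target.

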13.1.12 Methotrexate Minimal Dose

The Minimal Dose of MTX will be 7.5mg weekly. If this is not tolerated, the MTX and folic acid will be stopped, with the option to commence LEF therapy.

13.1.13 Methotrexate Split-Dosing

Taking the prescribed dose of MTX generally requires the participant to take multiple tablets to achieve the dose required. These tablets can be taken either together or split over the day. Splitting the dose of oral MTX may improve bioavailability (46). Morning or evening administration is equally acceptable; some participants find morning administration more convenient, while other participants report that side-effects are less troublesome if MTX is taken in the evening. However, split-dosing, if undertaken, should be restricted to a single day of the week. MTX should *not* be taken on more than one day in a given week due to toxicity risk.

13.1.14 Duration of Treatment

The anticipated duration of MTX treatment will be 18 months from the baseline visit, but can be stopped at any time in the event of toxicity or from 3 months at Maximal Tolerated Dose in the event of inefficacy. After MTX has been stopped, the participant will commence LEF, unless contra-indicated.

13.1.15 MTX compliance

Where possible within the conduct of this trial, local systems and processes to reduce the risk of MTX dosing errors should be followed. For example, participants must be instructed on the importance of adhering to the once-weekly dosing. Therefore, when initiating MTX, it is usually recommended to discuss and agree with the participant a specified day of the week that they will take their MTX. Where the participant is supported in the management of their condition by a family member or carer, with the consent of the participant the family member or carer must also be involved in these discussions.

Participants will be advised to maintain a record of their DMARD doses in addition to their steroid doses and provided with a personal diary for this if required. Details of DMARD compliance will be collected by the site research team during telephone and face-to-face assessments.

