Patients living with PMR confirmed that short and long-term health-related quality of life was a key consideration in their own decision-making around their own PMR treatment. They advised that monthly patient-reported outcomes (in the form of questionnaires) would not be excessively burdensome, as long as the questions were felt to be relevant to them. Patient and public contributors also suggested the idea of an additional “personal diary” that would be “owned” by the participant themselves, that could be shared with others if they chose.

Patients living with PMR had very diverse concepts of what PMR “relapse” meant to them, compared to the proposed definition based on current clinical practice that will be used as an inclusion criterion in this trial. While tapering prednisolone for PMR, patients adjust their steroid dose in response to changes in the severity of their PMR symptoms; cumulative steroid dose requirement is a key, quantifiable outcome that connects cumulative PMR disease activity and the combined effects of PMR and its treatment on health-related quality of life.

While this open-label trial is designed to be as pragmatic as possible, patients living with PMR reported substantial variation in care between different GPs, and advised that the study team might consider how they would ensure that minimum standards of care were adhered to within this trial sufficient to ensure participant safety in both trial arms, not just the DMARD arm. Since the trial was originally designed, “telemedicine” is increasingly utilised in both primary and secondary care, particularly for patients with stable disease or who find face to face medical appointments burdensome. The final trial design therefore incorporates regular scheduled telephone contact with the study team, in which adverse events can be identified and the site investigator and/or GP can be informed as appropriate.

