7.4.2 Questionnaires

Throughout the trial, participants will be asked to complete questionnaires, which will be returned to either by post or electronically.

Every 4 weeks, participants will be sent a questionnaire relating to their current steroid dose, steroid dosing over each of the preceding 4 weeks, and whether the steroid dose had to be increased due to worsening of PMR symptoms.

In addition, every 12 weeks they will be asked to complete a more extensive questionnaire pack relating to their PMR and treatment-related symptoms, health-related quality of life and healthcare resource use. The questionnaires to be included in these packs are listed in section 14.10

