13.3.11 Leflunomide compliance

Where possible within the conduct of this trial, local systems and processes to reduce the risk of LEF dosing errors should be followed.

Participants will be advised to maintain a record of their DMARD doses in addition to their steroid doses and provided with a diary for this if required. Details of DMARD compliance will be collected by the site research team during telephone and face-to-face assessments.

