16 OUTCOME MEASURES

16.1 PRIMARY OUTCOME MEASURE

The primary outcome measure is mean participant reported cumulative prednisolone dose between randomisation and 18 months post-randomisation, reported by participants via a monthly questionnaire.

Where a participant receives an alternative steroid medication to prednisolone, the steroid dose will be converted to a “Prednisolone equivalent dose” prior to analysis.

Intercurrent events of interest are:

- Death – to be handled under a treatment policy strategy;
- Discontinuation of trial treatment (including crossover to other arm) – to be handled under a treatment policy strategy;

Although steroid diaries are a part of routine clinical care, we acknowledge a lack of data as to the accuracy of participant-completed steroid diaries as a means to track medication usage. We have identified only small-scale results, incompletely reported and for different populations, claiming that medication diaries have satisfactory test-retest reliability (62) and that comparable methods of medication use surveillance lead to similar reported adherence levels (63).

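### Advice to record steroid doses, and the offer of a diary, are written only for the DMARD arm, although self-reported steroid dose is the primary outcome in both arms

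*Protocol*

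**What the plan says.** Section 13.1.15 has participants taking methotrexate "advised to maintain a record of their DMARD doses in addition to their steroid doses and provided with a personal diary for this if required". Section 13.3.11 repeats the advice for leflunomide: participants are to "maintain a record of their DMARD doses in addition to their steroid doses and provided with a diary for this if required". Only participants randomised to usual care plus DMARD come under these two sections.

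The primary outcome (section 16.1) is the cumulative prednisolone dose that participants report themselves. Section 7.4.2 has them asked every 4 weeks for the current dose and for "steroid dosing over each of the preceding 4 weeks". Section 14.10 derives cumulative dose, relapse dates and steroid cessation dates from this questionnaire and interpolates where needed. The schedule is the same in both arms.

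Diaries are mentioned in two other places, neither specific to an arm. In the background, patient contributors "suggested the idea of an additional “personal diary” that would be “owned” by the participant themselves". Section 16.1 states: "Although steroid diaries are a part of routine clinical care, we acknowledge a lack of data as to the accuracy of participant-completed steroid diaries".

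**The concern.** Giving the dose for each of the last 4 weeks is a recall task, and a written record helps with it. If sites advise and equip one arm to keep that record and not the other, the accuracy and completeness of the reported dose may differ by arm. The trial is open-label (section 7.1), so differences in reporting are already a main threat to a self-reported endpoint. Section 19.4 says that missing items are not chased from participants and section 14.10 interpolates across gaps, so uneven completeness could also feed into the outcome. Relapse and cessation outcomes come from the same questionnaire and share the exposure. The estimated arm difference could then contain a reporting component as well as a treatment component.

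**Working it through.** **Where the advice appears.** The sections of the protocol that could carry it, side by side:

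| Section | Applies to | Advice to record doses, or diary offer |
|---|---|---|
| 7.3.1 Steroid management | both arms | none |
| 7.4.2 and 14.10 Questionnaires | both arms | none |
| 11.3 Post-randomisation actions | both arms, plus a DMARD list | none |
| 13 Treatment, Arms A and B | both arms | none |
| 14.5 Baseline | both arms | none |
| 13.1.15 Methotrexate compliance | DMARD arm | yes |
| 13.3.11 Leflunomide compliance | DMARD arm | yes |
| 5.4 Background | participants in general | diary reported as a patient idea; assigned to no arm |
| 16.1 Primary outcome | no arm named | diaries called routine; nobody instructed |

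**The plan's own figure (section 17).** Inputs: 30% reduction, CV 0.78, two-sided 5%, 90% power, 20% attrition, 1:1 allocation.
- Log-scale SD = √ln(1 + 0.78²) = 0.689.
- Log-scale effect = −ln(0.70) = 0.357.
- A two-sample t-test needs 80 per arm (power 0.902). 80 / 0.80 = 100 per arm, 200 in total, as stated.
- At CV 0.94 the log SD is 0.796 and power with 80 per arm is 0.804, which agrees with the statement of at least 80%.
- Smallest observed reduction reaching p < 0.05 with 80 per arm: 1 − exp(−1.975 × 0.689 × √(2/80)) = 19.4%.

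**What a reporting difference would do (assumption only).** Suppose usual care reports its dose by a factor r relative to the DMARD arm. The apparent ratio is then 0.70 / r when the true ratio is 0.70, and 1 / r when there is no effect. With 80 per arm and CV 0.78:

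| r | Apparent ratio (true 0.70) | Power | Rejection rate, no true effect |
|---|---|---|---|
| 0.90 | 0.778 | 0.63 | 0.16 |
| 0.95 | 0.737 | 0.80 | 0.075 |
| 1.00 | 0.700 | 0.90 | 0.05 |
| 1.05 | 0.667 | 0.96 | 0.073 |
| 1.10 | 0.636 | 0.99 | 0.14 |

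For scale, 5% of the 5 g mean in section 17 is 250 mg. That section equates 1.5 g with 2.7 mg daily, so 250 mg is 2.7 × 250 / 1500 = 0.45 mg daily, averaged over every usual-care participant. The documents supply no value of r, and nothing in them shows whether it would lie above or below 1.

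**The case against.** A reader might infer that the primary outcome is measured with an aid in one arm only. The documents do not support that.
- Both arms complete the same questionnaire on the same 4-week cycle, and steroid use is also reviewed at calls and visits in both arms.
- The diary is offered only if required, and no section names it as a data source.
- The sentence in 13.1.15 and 13.3.11 can be read as adding DMARD doses to a steroid record that participants already keep. Section 16.1 supports that reading by calling steroid diaries routine, and both arms continue usual care.
- The recall period is at most 4 weeks and the current dose is asked each time. A dose rise lasting 4 weeks would normally overlap a questionnaire date, so forgetting it entirely is unlikely.

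All of this stands, and it limits the point. It does not remove it. The remark in section 16.1 instructs nobody and supplies nothing, and it goes on to concede that diary accuracy is not established. The background reports substantial variation in care between GPs, so uniform diary use cannot be assumed. An identical form does not equalise recall if only one arm is prompted to keep notes.

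It would also be too strong to say that the documents offer no check at all. Cumulative prescribed dose from GP records is a planned secondary outcome that does not depend on recall. It is an imperfect check: it counts prescriptions issued, not doses taken, and section 12.6 makes the site rheumatologist responsible for prescribing the prednisolone taper.

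**Conclusion.** The point holds in a limited form. Advice to record doses, steroid as well as DMARD, and the diary offer are written only for the DMARD arm. A site following the text would promote an optional recall aid in one arm of an open-label trial with a self-reported primary outcome. Reporting error could then differ by arm.

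The protocol does not say that usual-care participants keep no record or are refused a diary, and that should not be read into it. Direction and size are unknown. The 5% and 10% scenarios rest on an assumed average difference across a whole arm and show sensitivity, not expected bias. Differences of that order lie well below both the 19% smallest significant reduction and the 30% target, so they could not by themselves produce the target effect, but they would shift power and type I error noticeably. The sample size calculation reproduces and needs no change. This is an inexpensive improvement that works only prospectively, because recall cannot be equalised afterwards.

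**What to change.** In section 14.5, give every participant the same advice to record steroid doses and the same diary offer at the baseline visit, before allocation is known. After randomisation, add a DMARD page for Arm B. Limit sections 13.1.15 and 13.3.11 to DMARD doses.

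Cost: one wording change, about 100 more diaries if every usual-care participant takes one (half of 200; about 25 of them among the 50 Australian participants), and slight extra effort for those participants.
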